## 3.6 Sample size

The sample size of n = 60 per group is based on an initial estimation of the potential clinically relevant effect and variance as part of the preceding FORECEE project: a total of 60 participants are required to detect a difference of 0.2 in DNA methylation indices (e.g. WID-BC index), assuming a standard deviation of 0.44, at a statistical power of 0.94 and a significance level of 0.05. There are no preliminary data for longitudinal changes in the WID scores, thereby TirolGESUND acts as a pilot study to define effect sizes and variance for larger prospective studies in the future.

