# 5.4 Definition of primary, secondary, and subsidiary endpoints

#### 5.4.1 Primary objective

To assess whether a reduction/cessation in risk exposure (smoking, continuous non-timerestricted calorie intake resulting in being overweight/obese) via lifestyle modification over six months results in significant absolute changes in DNA methylation-based disease risk and ageing scores compared to baseline in cervical samples. Scores of the following age signatures will be evaluated:

- signatures that have previously been published, including
  - WID-BC
  - WID-OC
  - WID-EC
  - WID-CIN
  - WID-REA
  - WID-RIA
  - pcgtAge
- signatures that are not yet published but have been developed by the study group
  - Group of markers indicative of (stem) cellular age, e.g. WID-PCGT (general/immune/epithelial),
    WID-SEN (general/immune/epithelial), WID-PRO (general/immune/epithelial),
    etc. thereafter referred to collectively as "WID-SOLA"
- signatures indicative of exposure, e.g.
  - WID-SMK smoking index

Successful completion relates to a significant reduction in two ore more risk scores with no significant in increase in any of the scores.

Analysis will be conducted both ITT, intention to treat, and PP, per protocol, comparing baseline and month 6. ITT analysis may be conducted as a mixed-effects models, using compliance score as a covariate. A per protocol analysis may be conducted either by median compliance rate above or equal to 80%, or alternative split by mean or median compliance rate (see Figure 1).

Subgroup analyses will also be conducted as follows:

- 1. smoking cessation study arm: investigation of the impact of the use of electronic cigarettes on smoking signature scores
- 2. intermittent fasting study arm: investigation of difference between individuals who received ketogenic supplement and those that did not at 6 months
- 3. intermittent fasting study arm: subgroup analysis by fasting pattern (breakfast or dinner skipping)

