#### General study characteristics

• dropout rate

Is the dropout rate consistent with the literature (approximately 15-20% for lifestyle

interventions)? The analysis will be reported separately for the two sub-studies and randomised trial arms.

- *compliance* What is the compliance across the two sub-studies?
- sign-up rate

Out of participants that originally registered interest, how many wanted to finally participate and how many were included after meeting the criteria?

Moreover, the study will describe longitudinal alterations in a variety of health parameters (see also Fig. 2):

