#### 6.4.3 Primary endpoint reporting

For primary endpoint analysis, paired Wilcoxon tests will be performed on adjusted WID scores associated with disease risk, cellular ageing, or exposure, in cervical samples at baseline and month 6 of the intervention (adjusted for immune cell composition). For visualisation, points and lines may be coloured by compliance score, delta BMI, or smoking status at the end of the intervention. Data will be visualised using Spaghetti plots and may additionally be visualised using violin/box plots with overlayed jitter plots.

Analyses will be presented separately per sub-study and a comparison between the two randomised arms in the diet intervention study may be conducted. The analysis is predominantly conducted ITT, but separate subgroup analyses may be conducted as follows:

- $\bullet$  per protocol, if at least 30 individuals have a cumulative compliance score of more than 80%
- diet intervention: timing of fasting, breakfast versus dinner cancellation

Mixed-effects models could provide a complimentary method of reporting individual effects over time.

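### The stated power of 0.94 needs 60 complete pairs and an unsupported SD of change; at the dropout the SAP cites, a 60-woman group has about 0.85 to 0.89 per score

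*SAP*

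**What the plan says.** Section 3.6 (Sample size) contains the only power calculation in the SAP. It opens with "The sample size of n = 60 per group is based on an initial estimation" from a preceding project. The size of effect is that of a single index: "a total of 60 participants are required to detect a difference of 0.2 in DNA methylation indices (e.g. WID-BC index". The remaining inputs of the calculation are given as follows: "assuming a standard deviation of 0.44, at a statistical power of 0.94 and a significance level of 0.05". The section then adds a limitation: "There are no preliminary data for longitudinal changes in the WID scores". It names no test, no sidedness, no type of SD and no allowance for dropout.

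Four other places bear on how the figure can be used:

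- Section 5.4.2 (General study characteristics) gives the literature dropout rate as "approximately 15-20% for lifestyle" interventions.
- Section 6.4.3 fixes the primary test: "For primary endpoint analysis, paired Wilcoxon tests will be performed on adjusted WID scores", in cervical samples, baseline against month 6, presented per sub-study.
- Section 3.1 sets the sub-studies at 60 women (smoking cessation) and 120 women (diet, two randomised groups of 60).
- Section 5.4.1 defines success over a list of scores: "Successful completion relates to a significant reduction in two ore more risk scores with no significant in increase in any of the scores". It also lists the comparison of women with and without the ketogenic supplement among the subgroup analyses.

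**The concern.** A before-after comparison is powered by the number of complete pairs and by the SD of the within-woman change. Section 3.6 appears to count every enrolled woman as a pair, while section 5.4.2 cites a dropout rate that would remove 9 to 12 of 60. It also uses an SD whose type is not stated, in the same paragraph that says no longitudinal data exist. If 0.44 describes variation between women, the calculation contains a within-woman correlation that nobody has written down.

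At stake is how a null result is read. A score that does not change significantly in the smoking sub-study would be judged against a 6% chance of missing a true difference of 0.2. At the cited dropout that chance is 11-15%, and it could be considerably larger or smaller depending on the SD. Because 0.94 is the only power figure and its scope is not stated, it may also be carried over to analyses that it does not describe.

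**Working it through.** **Inputs.** Difference 0.2, SD 0.44, alpha 0.05, power 0.94, n = 60 (section 3.6); dropout 15-20% (section 5.4.2); sub-study sizes 60 and 120 (section 3.1); paired Wilcoxon test (section 6.4.3). Sidedness is not stated.

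**1. Reproduce 0.94.** Standardised change = 0.2/0.44 = 0.4545.

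- Normal approximation, two-sided: Phi(0.4545 × √60 − 1.96) = Phi(3.521 − 1.96) = 0.941.
- Solved for n: [0.44 × (1.960 + 1.555)/0.2]² = 59.8, so 60.
- Paired t (noncentral t), n = 60: 0.934.

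Other readings do not reproduce it: one-sided gives 0.967-0.970, two groups of 30 give 0.42, and two groups of 60 give 0.70. The figure is therefore two-sided, paired, for one score, with 60 complete pairs and 0.44 as the SD of the change.

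**2. Apply the cited dropout to a group of 60.** 60 × 0.85 = 51; 60 × 0.80 = 48. The Wilcoxon column uses its efficiency of 0.955 under normality, that is, the paired t power at 0.955n.

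| Pairs | Normal approx. | Paired t | Wilcoxon |
|---|---|---|---|
| 60 | 0.94 | 0.93 | 0.92 |
| 51 | 0.90 | 0.89 | 0.87 |
| 48 | 0.88 | 0.87 | 0.85 |

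**3. Diet sub-study, both arms pooled.** 120 × 0.85 = 102; 120 × 0.80 = 96. Paired t power is 0.999 at 120, 0.995 at 102 and 0.993 at 96; the Wilcoxon approximation at 96 is 0.99.

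**4. The SD.** If 0.44 is the SD between women at one time, with equal SDs at both visits, then SD of change = 0.44 × √(2(1 − r)), where r is the within-woman correlation. Only r = 0.5 returns 0.44.

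| r | SD of change | Power, 60 pairs | Power, 48 pairs |
|---|---|---|---|
| 0 | 0.622 | 0.69 | 0.59 |
| 0.3 | 0.521 | 0.83 | 0.74 |
| 0.5 | 0.440 | 0.93 | 0.87 |
| 0.7 | 0.341 | 0.99 | 0.98 |

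The 0.99 for the pooled diet sub-study has the same dependence. At r = 0 the variance doubles, so 96 pairs act like 48 pairs at SD 0.44, and power is about 0.88.

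**5. The success rule.** Section 5.4.1 names 7 published scores and WID-SMK (8), or 17 if the nine named WID-SOLA variants (three families in three forms) are counted. The list is open-ended, so both counts are a reading of it. The simulation used unadjusted two-sided tests at 0.05 per score, equal correlation of 0 to 0.7 between scores, and a true fall of 0.2 where a score changes.

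- Exactly two of 17 fall: 0.63-0.84 with 60 pairs, 0.58-0.79 with 48.
- Exactly two of 8 fall: about 0.77-0.87 with 60 pairs, about 0.69-0.80 with 48.
- All fall: 0.97 or more, even with 48 pairs.

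**6. The between-arm supplement comparison.** The SAP gives no between-arm difference or SD, so 0.2 and 0.44 are assumed here. With 60 per arm: 0.2/(0.44 × √(2/60)) = 2.49, and Phi(2.49 − 1.96) = 0.70; by two-sample t it is 0.69. With 51 and 48 per arm, two-sample t gives 0.62 and 0.60.

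**The case against.** The figure is not miscomputed. Section 3.6 ties it to 60 participants and to one index as an example. Section 2.1 warns that power may fall short for individual measures, section 3.1 calls the study predominantly exploratory, and section 3.6 calls it a pilot and openly discloses the lack of longitudinal data. The dropout range is posed as a question about consistency with the literature, not as a planning assumption; section 3.3 provides weekly coaching to limit attrition, and sections 3.11 and 5.3 keep sampling women who do not comply. Even after the full 15-20%, per-score power stays at 0.85 or above, and the SD point cuts both ways.

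Most of this stands, and it limits the point to scope and assumptions. It does not remove it. The coaching is described without a lower expected dropout rate, and a general caveat does not tell the reader which SD was used or that 60 means complete pairs.

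Three stronger readings are tempting but not supported. A reader might infer that the whole trial is underpowered; primary analyses are per sub-study (sections 3.10, 6 and 6.4.3), and the diet sub-study has 120 women. (Section 5.2 speaks of study arms, which leaves some ambiguity.) A reader might infer that the chance of meeting the success rule is well below 0.94; it depends on how many scores truly change and on their correlation, so it is undetermined. A reader might infer that the SAP claims 0.94 for the randomised contrast; it does not. Section 3.7 frames every null hypothesis as baseline against month 6, and the supplement comparison is a subgroup analysis.

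**Conclusion.** The point holds as a matter of unstated scope, missing dropout allowance and an unsupported SD, not as an arithmetic error.

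- If the cited 15-20% dropout applies and the SD of change is 0.44, the smoking sub-study, or one fasting arm alone, has per-score power of 0.87-0.89 by paired t and about 0.85-0.87 by Wilcoxon. The pooled diet sub-study has 0.99 or more.
- The larger uncertainty is the SD. If 0.44 is cross-sectional, power at 60 pairs runs from 0.69 (r = 0) to 0.99 (r = 0.7), and 0.94 rests on an unwritten r of 0.5.
- 0.94 does not describe the success rule: about 0.58-0.87 with 48-60 pairs if exactly two of 8 to 17 scores fall by 0.2, and 0.97 or more if all do, unadjusted. Nor does it describe the supplement comparison: about 0.69 at 60 per arm and 0.60-0.62 at 48-51, with the same difference and SD assumed.

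The Wilcoxon figures assume normally distributed changes.

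**What to change.** Leave the sample size as it is and revise section 3.6 as follows:

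1. Keep 0.94 only as the basis on which 60 was chosen, and describe it as a two-sided paired calculation for one score with 60 complete pairs.
2. State whether 0.44 is an SD of within-woman change or an SD between women. If it is the latter, say that 0.94 assumes a correlation of 0.5, and give power over a range of correlations such as 0 to 0.7.
3. Give per-score power by sub-study at the expected evaluable number, for the Wilcoxon test that section 6.4.3 plans: 48-51 pairs for smoking cessation (and for a single fasting arm), 96-102 for the pooled diet sub-study.
4. Add a sentence that 0.94 does not apply to the success rule in section 5.4.1 or to the supplement comparison, with the scenario-based figures for the rule and the approximate power of the between-arm contrast, each with its assumptions.

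The cost is a short rewording of one section and a less favourable stated figure for the smoking sub-study. No design, test or recruitment target changes.

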#### 3.7 Hypothesis framework

For each of the primary, secondary, or subsidiary outcomes, the null hypothesis is that there is no true difference in effect between the baseline measurement and the measurement taken at 6 months.

#### 3.8 Blinding

This is an open-label study. While the study is in progress, access to results of key study outcomes will not be available to the research team, trial statisticians, or other research collaborators.

#### 3.9 Timing of interim analyses

No interim analysis is planned for the TirolGESUND study.

# 3.10 Timing of analysis

The analysis of primary endpoints will be conducted collectively per sub-study once all samples and data become available for month 6 (main endpoint).

Secondary endpoints may be evaluated separately if data become available at a later timepoint, after initial investigation of the primary endpoints.

# 3.11 Timing of participant visits

Outcomes will be assessed using samples collected at the following timepoints:

- Baseline, including sports medicine examination and vascular analysis. All baseline measurements should be taken within 10 days of inclusion in the study, where feasible.
- Month 2 (7-10 weeks after inclusion)
- Month 4 (16-19 weeks after inclusion)
- Month 6 (25-28 weeks after inclusion)
- Month 12 (optional; 50-55 weeks after inclusion)
- Month 18 (optional; 75-79 weeks after inclusion)

Given practical limitations including annual leave, participant or staff illness, or other unforeseen circumstances, sample and data collection may be conducted outside these windows at the nearest possible date.

Baseline and regular outcome information will be collected in a trial-specific electronic case report form (eCRF), Askimed, by a member of the hospital or research staff at 2, 4, and 6 months of the study regardless of whether the participant is compliant with the intervention or not, although compliance will be monitored via regular check-ups by the coaches, biological measurements, and during study visitations. There are two optional follow-ups at 12 and 18 months. These will not be analysed with regards to primary endpoint but may inform stability of epigenetic changes for follow-up studies.

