# 3 Study methods

#### 3.1 Study design

TirolGESUND is a single-centre, open-label baseline-controlled study that encompasses two parallel arms with 6 months of intervention. One study is aimed at investigating the effect of smoking cessation. The other study is a randomised trial that evaluates the effect of intermittent fasting with or without ketogenic supplement. The two sub-studies will be evaluated separately. The study does not include a control group but instead investigates changes compared to baseline. Individuals that do not comply with the intervention but continue to provide samples may be utilised as a nested control group. The study is predominantly of exploratory nature, although comparisons to baseline measurements will be made as outlined in the primary, secondary, and subsidiary objectives. We aim to include a total of one-hundred and eighty participants as follows:

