# 5 Statistical principles

# 5.1 Significance levels and adjustment of p-values for multiplicity

Significance levels throughout are set at p < 0.05. Formal adjustment for primary and secondary outcomes may be conducted using Benjamini-Hochberg or Bonferroni correction as appropriate, although formal adjustments may not be strictly necessary for outcomes of more exploratory or descriptive nature, as previously argued. For subsidiary outcomes, no formal correction will be applied. 95% confidence intervals will be presented for estimates of effects throughout.

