# 6 Analysis

Analyses will be conducted and reported separately per sub-study (i.e. smoking cessation and intermittent fasting) after all samples for the month 6 timepoint have been collected. Key analyses will be performed on the ITT population. A per-protocol analysis will be conducted if sufficient individuals are available with above 80% compliance (n=30), or alternatively and additionally a subgroup analyses split by median compliance score (above and beyond, respectively). Descriptive statistics of dynamics over 6 months without an intervention will be reported and if sufficient individuals are present per study arm (n  $\geq 10$ ) that did not adhere, these may be used as a nested control group; although this number is small, it could be informative for dynamic changes without intervention.

The longitudinal manner of data collection enables baseline-controlled pairwise comparison (paired t or Wilcoxon test) for each participant at baseline and after 6 months; linear mixed effects-models may also be employed. Longitudinal dynamics and repeated measurements per participant, evaluating data from baseline, 2, 4, and 6 months, will be assessed using linear (or non-linear) mixed-effects models to account for inter-individual heterogeneity and differences in response (random intercept and slopes, if appropriate). In the intermittent fasting group, cross-sectional analyses may be used to compare effects for use with and without ketogenic supplement. Change from baseline may be reported in a descriptive manner.

Methylation data will be adjusted for sample cell type composition which is known to influence methylation levels. Many of the assessed factors are influenced by age. Dependence on other, non-intervention related covariates will be investigated during the exploratory data visualisation and assessment, and factors may be associated as covariates in mixed-effects models if necessary.

If a number of participants does not adhere to the intervention but continues to provide samples and the assumption of common support holds, we may be able to explore the average treatment effect (ATE) and causal average treatment effect (CATE) using causal inference (g methods) via covariate adjustment for selected secondary outcomes (in particular longitudinal DNA methylation analyses).

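### With no control group and a half-year gap between baseline and month 6, an annual cycle can pass for an intervention effect if enrolment is uneven over the year, and no calendar term is planned

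*SAP*

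**What the plan says.** Section 3.11 sets the main follow-up at "Month 6 (25-28 weeks after inclusion"). Section 3.1 states: "The study does not include a control group but instead investigates changes compared to baseline". The null hypothesis in section 3.7 is that there is "no true difference in effect between the baseline measurement and the measurement taken at 6 months". Section 6 says that the longitudinal data collection "enables baseline-controlled pairwise comparison (paired t or Wilcoxon test) for each participant at baseline and after 6 months".

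For the primary endpoint, section 6.4.3 says that "paired Wilcoxon tests will be performed on adjusted WID scores", with adjustment for immune cell composition only. The same paired before-after comparison is planned for clinical outcomes (6.5.3) and blood outcomes (6.7.2).

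The example models in section 6.4.4 list compliance, sample type, BMI or smoking status, cell composition and baseline age. Further covariates are optional and chosen during exploration (sections 6 and 6.4.4). Time may be coded as days since baseline (5.2), which is not calendar date. Processing date appears in 6.4.1, but only as a check for laboratory batch effects. Season, calendar date of sampling and the enrolment calendar are not mentioned anywhere in the SAP.

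**The concern.** Pairing removes stable differences between women. It does not remove a shift that the calendar imposes on many women at once. If most women enter in one season, most month 6 samples fall in the opposite season, and the paired change contains a seasonal component as well as any intervention effect. Without a concurrent control, the planned paired test cannot tell the two apart. The seasonal part could be reported as benefit or harm, in either direction.

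Several outcomes tested in this way could plausibly vary over the year: daily steps, active minutes, fitness, BMI, lipids and immune cell subsets. That list is our judgement; the SAP does not call any outcome seasonal.

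**Working it through.** **Inputs from the SAP.** Interval 25-28 weeks (3.11). "The sample size of n = 60 per group" is chosen "to detect a difference of 0.2 in DNA methylation indices" with a standard deviation of 0.44 and power 0.94 (3.6). "Significance levels throughout are set at p < 0.05" (5.1); two-sided testing is assumed.

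**Inputs assumed.** The amplitude A of the annual cycle (half the peak-to-trough swing) and the enrolment window of w months. The SAP gives neither.

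**Step 1: the plan's own figure.** The standard error is 0.44/√60 = 0.0568. Power is Φ(0.2/0.0568 − 1.96) = Φ(1.56) = 0.941 by the normal approximation, and 0.934 by the paired t test. The stated 0.94 is therefore reproduced as a one-sample or paired calculation, with 0.44 acting as the standard deviation of the change. A two-sample calculation with 60 per arm gives 0.70 and does not fit.

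**Step 2: phase.** 25 weeks is 25 × 7/365.25 × 360° = 172.5° of the year, and 28 weeks is 193.2°. The largest within-person change is 2A·|sin(half the phase)|, which is 2.00A at 25 weeks and 1.99A at 28 weeks. This is practically the largest difference an annual cycle can produce. At month 12 (50-55 weeks) the same formula gives 0.26A to 0.34A.

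**Step 3: bias in the group mean.** Take a half-year lag and even entry over w months, centred on the peak or trough (the worst case). The mean change has size 2A·|sin(x)/x|, with x = πw/12.

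| Enrolment window | x | \|sin(x)/x\| | Worst-case bias |
|---|---|---|---|
| 3 months | 0.785 | 0.900 | 1.80A |
| 6 months | 1.571 | 0.637 | 1.27A |
| 9 months | 2.356 | 0.300 | 0.60A |
| 12 months | 3.142 | 0 | 0 |
| 18 months | 4.712 | 0.212 | 0.42A |

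**Step 4: what this would do to a 5% test.** For illustration, take a score with standard deviation of change 0.44, n = 60 and no true effect, and use the noncentral t distribution. The noncentrality is bias/0.0568; for example, A = 0.05 over 3 months gives 0.090/0.0568 = 1.59.

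| Window | A = 0.02 | A = 0.05 |
|---|---|---|
| 3 months | 9.6% | about 34% |
| 6 months | 7.3% | about 20% |
| 9 months | 5.5% | 8.1% |
| 12 months | 5% | 5% |

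A = 0.05 is a quarter of the 0.2 difference that the study is sized to detect. If the two diet arms are pooled (n = 120), A = 0.05 gives about 60%, 35% and 12% for 3, 6 and 9 months.

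**Step 5: can a season term be estimated?** In a model with visits 0, 2, 4 and 6 as categories, participant effects and evenly spaced entry, sine and cosine terms multiply the standard error of the month 6 change by 1.00 (12-month enrolment), 1.07 (9 months), about 1.5 (6 months) and about 3.3 (3 months).

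**The case against.** A reader might infer that a seasonal swing is necessarily counted as intervention effect, including in the primary test. The SAP does not support that, for three reasons.

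- Bias in the mean needs uneven enrolment. With even entry over whole years the shifts cancel and only add variance. The enrolment calendar may stand in the protocol, which is not at hand. Smoking cessation groups of 6-12 women (3.3.1) imply 5 to 10 courses for 60 women, which suggests staggered entry without proving it.
- Nothing in the SAP shows that cervical WID scores vary by season. One imaginable route, a seasonal shift in the immune fraction, is largely what the planned cell-composition adjustment removes.
- The illustrative error rates rest on an assumed amplitude and worst-case timing. Section 3.6 itself says that there are no preliminary data on longitudinal change in these scores.

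The SAP also has partial checks. Six-month dynamics in non-adherers will be described (5.3, 6), and compliance will be modelled (5.2). Season would not create a compliance gradient if compliers and non-compliers share enrolment dates. The randomised ketogenic contrast (5.4.1) is largely protected because both arms share the calendar. Month 12 samples fall near the baseline season.

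These points weaken the concern but do not remove it. Non-adherers may be few, and their use as a control group is optional. The ketogenic contrast addresses only the supplement, and the smoking study has no equivalent. Month 12 is optional and outside the primary endpoint. A season covariate is permitted but not planned.

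Finally, the missing control is acknowledged and justified in 5.3, and the study is labelled exploratory. That is fair, but a season check is possible within this design.

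**Conclusion.** The point holds in conditional form. The interval is half a year, there is no concurrent control, and no calendar term is prespecified. If enrolment is uneven over the year, an outcome with an annual cycle will therefore carry a seasonal component in its mean change, which the planned paired test cannot separate from the intervention. The worst-case size runs from 1.80A for 3-month enrolment to 0 for enrolment spread evenly over 12 months. These figures assume a sinusoidal annual cycle and even entry within the window. The existence, sign and size of any actual bias cannot be determined from the SAP.

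The concern applies mainly to activity, fitness, BMI and blood outcomes. It is not evidence that the primary cervical result is biased. It is a worthwhile low-cost addition to the plan and not an error in what the plan states.

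**What to change.** Keep the primary paired test as it is, and add the following:

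1. Tabulate enrolment by calendar month for each sub-study.
2. Prespecify a sensitivity analysis that adds sine and cosine terms of sampling date (period one year) to the planned mixed models over months 0, 2, 4 and 6. Enter visit as a fixed categorical term; the example models in 6.4.4 have time only in the random part.
3. Report the month 6 change with and without these terms for the primary scores, physical activity, fitness, BMI and blood outcomes.
4. Use the optional month 12 samples descriptively as a near same-season check, with the caveat in 5.4.3 that highly compliant women may be more likely to return.
5. If enrolment covers only part of the year, state that season cannot be separated from the intervention.

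The cost is two model terms and one table, using sampling dates and no new data collection. The adjustment is least precise where it matters most. The standard error of the month 6 change is essentially unchanged for 12-month enrolment, but rises about 1.07-fold for 9 months, 1.5-fold for 6 months and 3.3-fold for 3 months. That is why it belongs in a sensitivity analysis and should not replace the primary test.
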